### 9.3 POOLING OF TRIAL CENTERS

Because of the potential of many trial centers to have a small number of patients, the centers will be pooled by the following 5 geographic regions (as listed in [Table 9.3-1](#)): Northeast, Southeast, Midwest, Southwest, and West. All analyses using trial center will use this 5-category center variable.

**Table 9.3-1 Definition of Geographic Regions**

Northeast	Southeast	Midwest	Southwest	West
CT	AL	IA	AZ	CA
DE	AR	IL	NM	CO
MA	FL	IN	OK	ID
MD	GA	KS	TX	MT
ME	KY	MI		NV
NH	LA	MN		OR
NJ	MS	MO		UT
NY	NC	ND		WA
PA	SC	NE		WY
RI	TN	OH		
VT	VA	SD		
	WV	WI		

### 9.4 DERIVED EFFICACY VARIABLES

#### 9.4.1 Patient Recall for eDiary Data

##### *Bowel Habits*

The eDiary is designed to allow patients to enter Daily Bowel Habits through a spontaneous report or the evening report.

The spontaneous report allows the patient to report BMs, occurring between evening reports, at any time. If the previous evening report was not completed, then the patient can report BM information occurring between 7:00 PM of the previous night and the current spontaneous report.

These BM information reporting rules were put into place to reduce recall bias.

### ***Rescue Medicine (RM)***

The spontaneous report allows the patient to report RM information, occurring between evening reports, at any time. If the previous evening report was not completed, then the patient can report RM information between 7:00 PM of the previous night and the current spontaneous report.

These RM information reporting rules were put into place to reduce recall bias.

### ***Abdominal Symptom Severity***

During the Evening Diary Report, the eDiary will capture separately the rating of abdominal pain, abdominal bloating, and abdominal discomfort experienced by the patient during the past 24 hours.

#### **9.4.2 Handling of Missing eDiary Data**

In the eDiary, for each BM and rescue medicine use reported, the patient will be asked whether the BM or rescue medicine use occurred “today” or “yesterday.” The following conventions will be followed in the event of missing data:

##### ***Gaps in the eDiary Data***

If a patient does not complete either a spontaneous or evening report every day, there will be gaps in the data.

There will be no adjustments for these gaps in the eDiary data for the efficacy data analyses using an OC approach. Effectively, this means that analyses will assume that no rescue medicine use or BMs occurred during these gaps.

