**Table 9.2-1 Analysis Time Windows for Efficacy Analysis**

Period	Analysis Week	Beginsa	Endsa
Pretreatment (Baseline b )	Week -2	Day -14	Day -8
	Week -1	Day -7	Day 1 (time of randomization)
Treatment	Week 1	Day 1 (time of randomization)	Day 7
	Week 2	Day 8	Day 14
	Week 3	Day 15	Day 21
	Week 4	Day 22	Day 28
	Week 5	Day 29	Day 35
	Week 6	Day 36	Day 42
	Week 7	Day 43	Day 49
	Week 8	Day 50	Day 56
	Week 9	Day 57	Day 63
	Week 10	Day 64	Day 70
	Week 11	Day 71	Day 77
	Week 12	Day 78	Day of last treatment period dose day c (usually Day 85)
RW	Week 1	RW Day 1	RW Day 7
	Week 2	RW Day 8	RW Day 14
	Week 3	RW Day 15	RW Day 21
	Week 4	RW Day 22	Day of last RW dose (usually day 28)

Note: There is no Day 0 or Week 0. For eDiary assessments in which a patient is asked to report if an event occurred “yesterday” or “today” (e.g., a bowel movement or rescue medication use), these windows pertain to when the event occurred, not to when the event is reported. For example, if a patient reports in eDiary on Day 78 a bowel movement occurring “yesterday,” that bowel movement (and subsequent stool consistency and straining scores) would be included in Analysis Week 11, not Analysis Week 12.

- a Relative to the date of randomization or first RW dose; Day 1 = the day of randomization; RW Day 1 = the day of first RW dose. For the calculation of rates (eg, stool frequency rates) in which the duration of a week or the overall period is calculated to the nearest hour, a day begins and ends at midnight.
- b Baseline values for efficacy parameters will be derived from the daily eDiary and eCRF data collected in the Pretreatment Period, specifically the period from 14 days before randomization up to the time of randomization.
- c For patients who fail to provide the date of last dose at the last visit, the later date of the last known dose (drug dispense eCRF) or the last eDiary date will be used to impute the last dose date.

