For the Treatment Period or RW Period, diary day is calculated as diary date – date of randomization or date of first RW dose + 1. For the Pretreatment Period, diary day is calculated as diary date - date of randomization. However, the day of randomization is always trial Day 1. Patients will complete their diary entries once a day, with the exception of Day 1 of entry into the Treatment Period, during which 2 diary data sets will be collected. On Day 1, daily questions will be entered before and after the randomization, whereas weekly questions will be entered before but not after randomization.

If a patient withdraws during the Treatment Period or RW Period, the patient's Treatment Period or RW Period shall end on the day of the last dose. The affected Treatment Period or RW Period week shall be shortened to the end of the withdrawn patient's Treatment Period or RW Period, and all subsequent Treatment Period or RW Period weeks will be missing for that patient.

**Table 9.2-2** presents the analysis weeks assigned for the efficacy analysis of the patient diary data related to Weekly Questions (e.g., Weekly Patient Assessment of Constipation Severity, Weekly Patient Assessment of IBS Symptom Severity, Weekly Patient and Assessment of Adequate Relief, and Weekly Patient Assessment of Treatment Satisfaction).

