### ***9.4.3.1 Length of an Analysis Week***

With respect to a patient's scheduled analysis weeks, the term *duration* is used. In regard to the *duration* of a week, it is expected that 1 or more of a patient's "weeks" may not be exactly 7×24 hours in duration (e.g., a patient may withdraw or discontinue early from the trial). Deviations from the 7×24-hour norm are structural in nature; and, as such, the calculations of the weekly rates of SBMs or CSBMs will incorporate the actual duration of the week.

Following an observed-cases approach, no adjustment to the duration of a week will be made for missing eDiary data absent because of missed reports.

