#### **9.4.3.2 Weekly Stool Frequency Rate Calculations**

The weekly frequency rate for SBMs (CSBMs) will be based on the number of SBMs (CSBMs) occurring during that week, adjusting for differences in the duration of the week versus the 7×24-hour norm. A description of the corresponding formula is provided below.

Weekly stool frequency rates for each analysis week will be calculated as follows:

$$\text{Weekly Frequency Rate (Analysis Week}_i\text{)} = (7 \times 24) \times C_i/D_i$$

Where:

$i$  is an indicator of analysis week number (e.g.,  $i = -2, -1, 1, \dots, 12$ ),

$C_i$  is the number of events (SBMs or CSBMs) reported during analysis week  $i$ , and

$D_i$  is the duration (in hours) of analysis week  $i$ , from beginning to end ([Table 9.2-1](#)).

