#### **9.4.3.3 Overall Weekly Stool Frequency Rate Calculations for Each Analysis Period**

For each of the analysis periods (Pretreatment [Baseline] and Treatment Period), the overall weekly stool frequency rates will be calculated in a manner similar to that for an individual week. The corresponding formulas are provided below.

Overall weekly stool frequency rates for each analysis period will be calculated as follows:

$$\text{Weekly Frequency Rate (Analysis Period}_j\text{)} = (7 \times 24) \times C_j/D_j$$

Where:

$j$  is an indicator of analysis period number (e.g.,  $j = 1$  [pretreatment], 2 [treatment]),

$C_j$  is the number of events (SBMs or CSBMs) reported during analysis period  $j$ , and

$D_j$  is the duration (in hours) of analysis period  $j$ , from beginning to end ([Table 9.2-1](#)).

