#### **9.4.4 Other Weekly Scores Derivation**

For the abdominal score, first the daily average of Abdominal Pain, Abdominal Bloating and Abdominal Discomfort will be calculated. If more than 1 of the symptom scores is missing on a day, that daily abdominal score will be missing. Weekly scores will be based on the average of the non-missing daily abdominal scores.

For Abdominal Score, Pain, Bloating, and Discomfort, the patient's weekly average will be the average of the non-missing daily scores reported by the patient during each week.

For stool consistency questions, the patient's weekly score will be the average of the non-missing daily scores from the SBMs reported by the patient during each week.

For straining, the patient's weekly straining score will be the average of the non-missing daily straining scores from the SBMs reported by the patient during each week.

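### Diary gaps count as zero bowel movements and zero rescue use over a full-length week, so an on-study week with no entries scores 0 SBM and 0 CSBM (additional endpoints only)

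*SAP*

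**What the plan says.** SAP 9.4.2 describes its treatment of diary gaps as an observed-case approach and spells out the consequence: "Effectively, this means that analyses will assume that no rescue medicine use or BMs occurred during these gaps".

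SAP 9.4.3.1 shortens a week for structural reasons such as withdrawal, but "no adjustment to the duration of a week will be made for missing eDiary data absent because of missed reports". SAP 9.4.3.2 then computes the weekly rate as (7 × 24) × C/D, where C is the count of SBMs or CSBMs and D "is the duration (in hours) of analysis week", from its beginning to its end. No minimum number of entries is set. For the baseline and Treatment Period, SAP 9.4.3.3 says that "the overall weekly stool frequency rates will be calculated in a manner similar to that for an individual week".

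Under SAP 9.2, when a patient withdraws, the "Treatment Period or RW Period shall end on the day of the last dose", and later weeks are missing. If the date of last dose is not provided, footnote c of Table 9.2-1 uses "the later date of the last known dose (drug dispense eCRF) or the last eDiary date"; SAP 9.6 is to the same effect.

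The abdominal symptoms are handled differently. Under SAP 9.4.4, "Weekly scores will be based on the average of the non-missing daily abdominal scores", so a week with no evening report has no Abdominal Score.

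**The concern.** In a gap the numerator receives nothing and the denominator keeps its calendar length. Two consequences follow.

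- **Silent weeks.** If a patient is still dosing but makes no diary entry for a whole week, C = 0 and D = 168 hours, so the rate is 0. No section sets that week to missing for the rate endpoints. The zero is not stated in words; it follows from 9.4.2, 9.4.3.1 and 9.4.3.2 read together. It sits badly with the observed-case label and with SAP 6.3, under which missing data are not imputed unless stated otherwise.
- **Partly reported weeks.** The rate is understated if bowel movements in the gap were neither entered as they occurred nor recovered later. Unreported rescue use works the other way: the next day's bowel movement then passes as spontaneous.

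The existing protections do not reach these endpoints fully. The rule requiring four evening reports (SAP 7.9) governs weekly responder status, and weeks with 4 to 6 reports pass it with a gap-affected CSBM rate. The multiple imputation (SAP 7.9.1.2) is for the primary and secondary endpoints. The compliance tables (SAP 7.8) would show unequal reporting but leave the rates as they are.

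Affected are change from baseline in SBM and CSBM rate; percent of days with rescue use, where the percentage itself can only be understated; the CSBM and APC +1 responders, through weeks with 4 to 6 reports and through baseline gaps; and the descriptive RW summaries.

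**Working it through.** The plan gives no figure for diary gaps, so there is none to reproduce. Its power statement (>99% and ~94%) rests on resampled data that the documents do not contain and concerns the abdominal-score hypotheses only.

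**Formula check (SAP 9.4.3.2).** Full week, 7 SBMs: 168 × 7/168 = 7.0. Withdrawal after 72 hours with 3 SBMs: 168 × 3/72 = 7.0. Structural shortening is handled correctly.

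**Whole-day gaps.** With a true 1 SBM per day and m days lost, the rate is 168 × (7 − m)/168. For m = 1, 2, 3, 5, 7 it is 6.0, 5.0, 4.0, 2.0, 0.0.

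**Unreported rescue.** Rescue on day 3 falls in a gap; the only bowel movement, on day 4, is reported. The true SBM rate is 0; the scored rate is 168 × 1/168 = 1.0. With 6 of 7 evening reports the week passes the four-report rule. If that movement was complete and the baseline CSBM rate is 0, it meets the +1 CSBM criterion by itself.

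**Baseline.** Protocol 6.1, item 11, allows up to 4 of 14 evening reports to be missed. If those days were wholly lost, a true rate of 1.0 per week is expected to be recorded as 1.0 × 10/14 = 0.71, overstating the change by 0.29. Baseline gaps precede randomization, so they do not bias the arm difference in expectation.

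**Arm difference.** Inputs: CSBM changes of 2.1 and 1.1 (Protocol 3.3, Phase 2b study); assumed baseline b = 0.5 per week, range 0.2 to 1.0; assumed fractions of on-treatment days wholly lost, gL for linaclotide and gP for placebo.

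Difference = (b + 2.1)(1 − gL) − (b + 1.1)(1 − gP)

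| gL / gP | b = 0.2 | b = 0.5 | b = 1.0 |
|---|---|---|---|
| 0 / 0 | 1.00 | 1.00 | 1.00 |
| 10% / 10% | 0.90 | 0.90 | 0.90 |
| 15% / 5% | 0.72 | 0.69 | 0.64 |
| 5% / 15% | 1.08 | 1.11 | 1.16 |

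For b = 0.5: 2.6 × 0.85 − 1.6 × 0.95 = 0.69, and 2.6 × 0.95 − 1.6 × 0.85 = 1.11. If half the movements on missed days were entered as they occurred, 15%/5% gives 2.6 × 0.925 − 1.6 × 0.975 = 0.845. If none were lost, it is 1.00.

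**Silent weeks.** With b = 0.5 each is recorded as a change of −0.5. One in 12 takes a patient's mean change from 2.1 to (11 × 2.1 − 0.5)/12 = 1.88. If 5% vs 2% of patient-weeks were silent (assumed), the difference is 2.6 × 0.95 − 1.6 × 0.98 = 0.90; with 2% vs 5% it is 2.6 × 0.98 − 1.6 × 0.95 = 1.03.

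**A rate on reported days only, at 15%/5% missed.** If days are missed at random it restores 1.00. If every missed day truly had no CSBM, it gives 2.6/0.85 − 1.6/0.95 = 1.37, where the SAP rate is correct at 1.00. If days with a CSBM are twice as likely to be missed, take Poisson counts, so that a day has no CSBM with probability exp(−2.6/7) = 0.690 or exp(−1.6/7) = 0.796. The chance that a CSBM day is missed is then 2 × 0.15/1.310 = 0.229 or 2 × 0.05/1.204 = 0.083. The SAP rate gives 2.6 × 0.771 − 1.6 × 0.917 = 0.54, and the reported-day rate 2.6 × 0.771/0.85 − 1.6 × 0.917/0.95 = 0.81. The truth of 1.00 lies above both, so the two are not bounds.

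**The case against.** The rule is prespecified and its consequence is disclosed. It touches only endpoints outside formal testing (SAP 7.9.3) and RW summaries without inference (SAP 7.9.4.1). Silence may mean that nothing happened, in which case zero is right. Reporting is also well supported: four evening alarms (Protocol 8.1.5), compliance checks and reminders at visits, and in-clinic diary entry. All of this stands, and it keeps the point minor. It does not supply a rule for a week with no data.

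Three stronger readings are tempting, and the documents do not support them.

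- A reader might infer that every missed evening report loses a day of bowel movements. Movements are entered as they occur, later entries can reach back to 7 PM of the previous night (SAP 9.4.1), and patients are asked whether an event was today or yesterday (SAP 9.4.2). The whole-day figures are upper cases.
- A reader might infer that anyone who stops the diary is scored zero through Week 12. Weeks after the last dose are missing, and a missing last-dose date is imputed as the later of the last known dose and the last eDiary date. Zero weeks therefore arise mainly with recorded dosing and no diary.
- A reader might infer that the primary result is at risk. It uses only abdominal scores, whose missing days stay missing.

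The opposite claim, that the four-report rule fully protects the responder endpoints, does not hold either, as the rescue example shows.

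**Conclusion.** The point holds and is minor. As written, the plan gives a patient who is dosing but silent for a week a score of 0 SBM and 0 CSBM while treating the same week as missing for the Abdominal Score. In partly reported weeks the error can go in either direction. Equal on-treatment losses shrink the arm difference; unequal losses can shrink or inflate it. The figures of 0.90, 0.69 (0.64 to 0.72) and 1.11 (1.08 to 1.16) against 1.00 are illustrations. They rest on assumed gap rates, an assumed baseline and whole-day loss; none of these is given in the documents. The primary endpoint, the secondary endpoints and the fixed sequence are unaffected.

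**What to change.** 1. In SAP 9.4.3, set the weekly SBM and CSBM rates, and likewise the weekly rescue-day percentage, to missing for any on-study Treatment or RW analysis week with no spontaneous and no evening report. Such weeks already count as non-response for responder endpoints based on daily diary data. No change to 9.4.3.3 is needed: no listed change endpoint uses the overall Treatment Period rate, and a patient with at least 10 of 14 baseline reports cannot have a silent baseline week.
2. Keep the current rate as the main analysis for all other weeks. Prespecify one sensitivity analysis of SBM and CSBM change that takes both count and duration only from days with a completed evening report, with the rate missing when a week has fewer than 4 such reports. Report both results as two assumptions, not as bounds.

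The cost is a little more SAP text, derivation and analysis. Step 1 assumes that silent weeks resemble reported ones: if 5% vs 2% of weeks were silent and truly had no bowel movement, it would give 1.00 where the truth is 0.90. The reported-day version discards movements entered on days without an evening report and can overstate if days without movements are missed more often (up to 1.37 above), so it should not replace the main analysis. Neither step corrects unreported rescue use in partly reported weeks.

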##### ***Missing “Today” or “Yesterday” Information for Rescue Medicine***

When a patient uses rescue medicine and the exact date of use is known, there will be a 2-day window during which any BMs will not be assessed as SBMs: (1) the day when the rescue medicine was administered and (2) the day after. If, in the daily diary, a patient has reported taking a rescue medicine but the corresponding date is missing, the rescue medicine use must have occurred either on the day of the diary entry or on the day before the diary entry. The rescue medicine window in this missing-date scenario will be 3 days, covering the day before the eDiary report, the day of the eDiary report, and the day after the eDiary report. This window will be used to determine if a BM should be considered an SBM.

For the analysis of rescue medicines, the missing date will be imputed as the date in which the rescue medicine was reported.

##### ***Missing “Today” or “Yesterday” Information for Bowel Movements***

If a patient reports having had a BM but does not provide the exact date, the BM must have occurred either on the day of the report or on the day before the report. For determining whether a BM is an SBM, this 2-day BM window will be used in conjunction with the rescue medicine window. If there is any overlap between the 2-day BM window and the patient’s rescue medicine window (which could be either 2-day window or 3-day window), the BM will not be considered an SBM.

Many analyses require specific dates for each BM. If a BM date is missing, it will be imputed as the date/time stamp of the eDiary report in which the BM was reported. However, the following exception applies to this imputation rule:

When the first day of the BM window is the last day of a rescue medicine window and the second day of the BM window is not also a day of a rescue medicine window, the missing BM date will be imputed as the first day of the BM window (i.e., the day before the eDiary report in which the BM was recorded). This rule of exception is designed to minimize the risk of mischaracterizing a non-spontaneous BM as an SBM.

### ***Missing Stool Consistency Questions***

No imputation will be performed for a missing BSFS score or the stool consistency 5-point ordinal measure.

### ***Missing Completeness of Evacuation Response***

If the completeness of evacuation response (Question #12) is missing, an SBM will not be considered complete.

### ***Missing Daily Abdominal Symptoms***

No imputation will be performed for missing daily abdominal symptoms (Abdominal Pain, Abdominal Discomfort, Abdominal Bloating).

## **9.4.3 Weekly Stool Frequency Rates**

The components for calculating a patient's stool frequency rates (BM, SBM, and CSBM weekly rates) for a given analysis week are as follows:

- The number of BMs that occurred during that analysis week
- The number of those BMs that were SBMs
- The number of those SBMs that were CSBMs
- The length of time of the analysis week

The determination of the length of time of an analysis week is provided in Section [9.4.3.1](#).

### ***9.4.3.1 Length of an Analysis Week***

With respect to a patient's scheduled analysis weeks, the term *duration* is used. In regard to the *duration* of a week, it is expected that 1 or more of a patient's "weeks" may not be exactly 7×24 hours in duration (e.g., a patient may withdraw or discontinue early from the trial). Deviations from the 7×24-hour norm are structural in nature; and, as such, the calculations of the weekly rates of SBMs or CSBMs will incorporate the actual duration of the week.

Following an observed-cases approach, no adjustment to the duration of a week will be made for missing eDiary data absent because of missed reports.

#### **9.4.3.2 Weekly Stool Frequency Rate Calculations**

The weekly frequency rate for SBMs (CSBMs) will be based on the number of SBMs (CSBMs) occurring during that week, adjusting for differences in the duration of the week versus the 7×24-hour norm. A description of the corresponding formula is provided below.

Weekly stool frequency rates for each analysis week will be calculated as follows:

$$\text{Weekly Frequency Rate (Analysis Week}_i\text{)} = (7 \times 24) \times C_i/D_i$$

Where:

$i$  is an indicator of analysis week number (e.g.,  $i = -2, -1, 1, \dots, 12$ ),

$C_i$  is the number of events (SBMs or CSBMs) reported during analysis week  $i$ , and

$D_i$  is the duration (in hours) of analysis week  $i$ , from beginning to end ([Table 9.2-1](#)).

#### **9.4.3.3 Overall Weekly Stool Frequency Rate Calculations for Each Analysis Period**

For each of the analysis periods (Pretreatment [Baseline] and Treatment Period), the overall weekly stool frequency rates will be calculated in a manner similar to that for an individual week. The corresponding formulas are provided below.

Overall weekly stool frequency rates for each analysis period will be calculated as follows:

$$\text{Weekly Frequency Rate (Analysis Period}_j\text{)} = (7 \times 24) \times C_j/D_j$$

Where:

$j$  is an indicator of analysis period number (e.g.,  $j = 1$  [pretreatment], 2 [treatment]),

$C_j$  is the number of events (SBMs or CSBMs) reported during analysis period  $j$ , and

$D_j$  is the duration (in hours) of analysis period  $j$ , from beginning to end ([Table 9.2-1](#)).

#### **9.4.4 Other Weekly Scores Derivation**

For the abdominal score, first the daily average of Abdominal Pain, Abdominal Bloating and Abdominal Discomfort will be calculated. If more than 1 of the symptom scores is missing on a day, that daily abdominal score will be missing. Weekly scores will be based on the average of the non-missing daily abdominal scores.

For Abdominal Score, Pain, Bloating, and Discomfort, the patient's weekly average will be the average of the non-missing daily scores reported by the patient during each week.

For stool consistency questions, the patient's weekly score will be the average of the non-missing daily scores from the SBMs reported by the patient during each week.

For straining, the patient's weekly straining score will be the average of the non-missing daily straining scores from the SBMs reported by the patient during each week.

